10.1.4.1. Treatment Visit 4.1/5.1 (28 days+1 week after TV4 or TV5)

The following procedures will be performed at the drug re-supply visit to be scheduled at the conclusion of the patient's study drug holiday:

- Collect completed questionnaires
- Record any changes in the usual PD medication dose/regimen.
- Record any changes in concomitant medications.
- Record any adverse events.
- Distribute new study drug kits.
- Review inhaler training with the patient (if needed).
- Distribute the PD Diary and Inhaled Dosing Log and review instructions for completion

10.1.5. Early Withdrawal Visit

Patients who withdraw prematurely will complete the TV6 assessments (see [Section 10.1.3.9](#)), except for the pre-TV6 DLco and spirometry assessments, at the time of withdrawal. In addition, patients will be scheduled the DLco and spirometry visit 4 to 5 weeks after completion of the Early Withdrawal Visit. The DLco and spirometry assessments should be performed in an ON state (as reported by the patient to the pulmonary technician) in the pulmonary function facility. As part of the procedure, a slow vital capacity maneuver will be first, followed by DLco, and then spirometry. Patients who withdraw prematurely and prior to participating in the sub-study to assess potential withdrawal symptoms will complete the withdrawal assessments during the 28 days following completion of the TV6 assessments (see [Section 10.1.4](#)).

10.1.6. Unscheduled Visits

An unscheduled visit may occur when indicated at the discretion of the Investigator. The following are potential circumstances for unplanned visits:

- For CVT-301-naïve patients, if concordance is not reached during SV1, the same training and testing may be repeated at an unscheduled visit between SV1 and SV2 or at SV2. If patients return for an unscheduled visit between SV1 and SV2 for concordance training and testing, the visit must occur more than 3 days prior to SV2.

- For CVT-301-naïve patients, if a patient is unable to complete a screening assessment at SV2 (repeat SV2), an additional visit may be scheduled prior to eligibility determination and randomization. Any repeat assessments should be performed in the respective motor state as described for SV1.
- If a patient develops significant tolerability concerns that in the opinion of the investigator are of a severity that should necessitate a reduction in dose, including, but not limited to, exacerbation or worsening of troublesome dyskinesia, other problematic dopaminergic symptoms, or other tolerability concerns, a dose reduction (from 2- to 1-capsule inhalation per dose) will be permitted. The medical monitor should be contacted, and the investigator should use his/her clinical judgment to determine if an additional unscheduled visit is required and what assessments should be performed (e.g., physical examination, spirometry, etc.).
- Patients who have completed TV5 at the time of implementation of protocol Version 5.2 will have the option to consent to this amendment at an Unscheduled Visit prior to TV6, at which time they will receive an additional 4 weeks of study drug so that TV6 can be scheduled for approximately 13 months (56±2 weeks) after TV1.

11. DESCRIPTION OF ASSESSMENTS

11.1. Safety Assessments

Safety will be assessed from physical examination, AE reporting, standard and orthostatic vital signs (BP, RR, and HR), clinical laboratory values (hematology and biochemistry), ECGs, and spirometry and DLco for evaluation of pulmonary function. In addition, UPDRS Part 4, and evaluations for assessing suicidality, somnolence, impulse control disorders, and withdrawal symptoms will be done.

11.1.1. Physical Examination

A complete physical examination (head, eyes, ears, nose, and throat [HEENT], heart, lungs, abdomen, skin, cervical and axillary lymph nodes, neurological, and musculoskeletal systems) will be performed at the visits specified in [Appendix 2](#) through [Appendix 10](#). Genital, rectal, and breast examination may be excluded if not clinically indicated. The physical examination will include height (cm) and weight (kg) only at screening. Physical examinations will be performed by a physician. In addition, medical history will be recorded at screening, including smoking history, if applicable.

A brief physical exam to verify continued patient eligibility and to follow up any change in medical history will be performed at visits specified in [Appendix 2](#) through [Appendix 10](#). Symptom-driven brief physical examinations will be performed as clinically indicated at any study visit. All changes identified as clinically noteworthy must be recorded as AEs.

11.1.2. Vital Signs

Standard Vital Signs

Vital sign measurements will include RR, BP (systolic [SBP] and diastolic [DBP]), and HR after the patient has rested in a supine or semi-supine position for at least 5 minutes.

Blood pressure must be assessed using an appropriate device, and the arm position must be standardized for each patient using a cuff size that is appropriate for the patient. These measurements are to be taken in the same arm for the duration of the study. The position of the cuff on the arm should be in line with the heart with the arm lying next to the patient when semi-supine and should be in line with the heart at approximately a 45-degree angle from horizontal for the standing measurements. “Standard” BP and HR measurements should be taken after resting in a supine or semi-supine position for at least 5 minutes.

Respiratory rate should be recorded for 30 seconds, and the value multiplied by 2 for the rate per minute.

Vital sign measurements will be repeated if clinically significant or machine/equipment errors occur. If out-of-range BP, RR, or HR results are observed, the assessments may be repeated at the investigator’s discretion. Any confirmed, clinically significant vital sign measurements must be recorded as AEs.

Orthostatic Vital Signs

At screening (SV1 or SV2) and at each subsequent study visit and in the event of a clinically significant finding that could be suggestive of symptomatic orthostatic hypotension (e.g., dizziness, lightheadedness, or other AE), orthostatic vital signs will be performed. During the orthostatic vital signs assessment, at least one other staff member familiar with the study (not measuring vital signs) must be present should symptoms or an AE occur.

In order to obtain orthostatic vital signs, patients should undergo the following procedures in sequential order:

1. After the supine/semi-supine BP and HR measurements have been done, the patient will be asked to sit on the edge of the bed/table with feet on the floor (or with feet dangling from the bed/tableside depending on the height of the bed/table) for approximately 30 seconds.
2. The person performing the assessment will then ask the question, “Are you ready to stand?”
 - If the patient responds in the affirmative, the patient will proceed to stand and then be asked to remain standing for 2 minutes. After standing for 2 minutes, BP and HR will be recorded.
 - If the patient states that he or she is not ready to stand, the patient will be allowed to sit as positioned for 1 additional minute and will be asked again if they are ready to stand. The patient will proceed to stand. After standing for 2 minutes, one measurement will be taken for BP and HR.
 - If the individual is still unable to stand, vital signs will be measured while the patient is in an upright seated position.

Orthostatic hypotension will be defined as a reduction in SBP of 20 mmHg or more, and/or a reduction in DBP of 10 mmHg or more, for the standing measurement compared to the semi-supine measurement. If orthostatic hypotension is suspected, the measurement process may be repeated at the investigator's discretion. Any changes of potential clinical concern will be recorded as AEs.

11.1.3. Electrocardiogram

Standard 12-lead ECGs will be obtained after the patient has rested in a supine position for at least 5 minutes. Electrocardiograms will be measured using an ECG machine that automatically calculates the HR and measures PR, QRS, QT, QT interval corrected using Bazett's formula (QTcB) and QT interval corrected using Fridericia's formula (QTcF).

Please refer to [Appendix 2](#) through [Appendix 10](#) regarding specific times of ECG assessments at individual study visits.

Electrocardiogram equipment will be provided to each study site to perform all assessments.

Electrocardiograms will be repeated if clinically significant abnormalities are observed or artifacts are present. Electrocardiograms will be reviewed by qualified staff and over-read by the Central ECG Laboratory.

11.1.4. Laboratory Parameters

Hematology, clinical chemistry, and additional laboratory parameters to be tested are listed in [Appendix 13](#). Patients do not need to be in a fasted state at the time of any laboratory sample; however, fasted status will be documented (with fasting defined as at least 4 hours following the last meal or snack).

Laboratory samples will be analyzed by a central laboratory [REDACTED] to ensure consistent interpretation of results. In the event of an unexplained clinically significant abnormal laboratory test value, the test should be repeated immediately and followed up until it has returned to the normal range and/or an adequate explanation of the abnormality is found.

11.1.5. Pregnancy Status

Women of child-bearing potential must have a negative pregnancy test (serum hCG test) at screening. A serum hCG test will be performed at screening (SV1 or SV2) for CVT-301-naïve patients and [CVT-301-009](#) patients, and at TV1, TV3, TV4, TV5, and TV6, if applicable.

If sexually active and the female is of child-bearing potential, the patient (and his/her partner) should use adequate contraceptive measures for the duration of the study. Adequate measures should consist of 2 forms of contraception (except in cases of surgical sterilization), at least 1 of which must be a barrier method (e.g., male partner uses condoms, plus female partner uses diaphragm and spermicidal gel, or cervical cap and spermicidal gel, or intrauterine device, or oral contraceptive pill).

Female patients found to be pregnant will be withdrawn from further treatment, but will be followed for the duration of their pregnancy.

11.1.6. Spirometry

The following is a description of the pulmonary function testing at clinical sites and at dedicated pulmonary function facilities:

Pulmonary function will be measured by spirometry using the guideline specified by the Third National Health and Nutrition Examination Survey (NHANES III) ([Hankinson 1999](#)). Spirometry (with the exception of spirometry being performed in conjunction with DLco) will be performed by trained and qualified staff at each study site. Spirometry data collected by the study sites will be reviewed by a central spirometry laboratory [REDACTED] which will provide a quality over-read of all evaluations based on acceptability and repeatability metrics in accordance with ATS criteria ([Miller et al., 2005](#)). FEV₁, FVC and FEV₁/FVC ratio will be recorded from the single “best test” (based on effort with highest summed FEV₁ and FVC). Variables and comparisons will include the actual and expected forced FEV₁, FVC, and FEV₁/FVC ratio. Patients with FEV₁ <50% of predicted for race, age, sex, and height, or FEV₁/FVC ratio ≤60% in the ON state at screening will be excluded from the study. A pulmonologist will review the spirometry tracings/morphology of any patient with an FEV₁ that is ≥ 50% to <60% of predicted or an FEV₁/FVC ratio that is >60% to <70% at screening in order to determine eligibility. Patients with an FEV₁/FVC ratio that is >60% to <70% at screening will complete spirometry before and after the administration of a bronchodilator in a pulmonary function laboratory. Testing will be performed in accordance with the 2005 ATS/European Respiratory Society (ERS) criteria. The results of the bronchodilator challenge will be reviewed by a pulmonologist prior to potential randomization. Any CVT-301-naïve patients or [CVT-301-009](#) patients requiring pulmonary adjudication at screening will not be randomized until after full pulmonologist review.

Spirometry assessments will be done at the time points indicated in [Appendix 2](#) through [Appendix 10](#). The patient’s motor state at the time of each spirometry assessment will be recorded. At SV1, spirometry assessments should be done while the patient is in both the ON and OFF states. At SV2, spirometry assessments will be done only if a repeat measurement is needed for assessing eligibility.

Spirometry equipment will be provided to each study site to perform all spirometry assessments for CVT-301-naïve patients and [CVT-301-009](#) patients at SV1, SV2 (if necessary) and TV1 (all patients). All other spirometry assessments will be collected during the DLco and spirometry visits that take place at the pulmonary function lab. Spirometry data collected at pulmonary function labs will be reviewed immediately by a pulmonologist on site for safety signals and then sent to and reviewed by a central Pulmonary Function Testing reviewer (TechEd Consultants).

11.1.7. Carbon Monoxide Diffusing Capacity (diffusing capacity of the lungs for carbon monoxide-DLco)

Patients will undergo DLco assessments, which will be acquired in accordance with ATS criteria ([Miller et al., 2005](#)), at a dedicated pulmonary function facility after SV2 (and prior to TV1; 301-naïve patients and [CVT-301-009](#) patients), within 2 weeks prior to TV3, TV4, TV5, and TV6, and at 4 to 5 weeks after TV6, as described in the [Appendix 3](#) through [Appendix 10](#). These assessments should be performed while the patient is in the ON state (as reported by the patient to the pulmonary technician). Pulmonary function facility technicians will perform a slow vital capacity maneuver, followed by DLco, and then spirometry. The pulmonary facilities will use

their own equipment to perform all necessary pulmonary function testing relevant to DLco acquisition.

DLco and slow vital capacity maneuvers will be assessed and processed in accordance with ATS/ERS standards. Spirometry procedures will be conducted at the same visits in the same manner as those conducted at clinical sites in accordance with ATS criteria (see [Section 11.1.6](#)).

All DLco data collected at pulmonary function labs will be sent to and reviewed by a central Pulmonary Function Testing reviewer (TechEd Consultants).

11.1.8. Adverse Events

An AE is any symptom, physical sign, syndrome, or disease that either emerges during the study or, if present at the start of the study, worsens during the study, regardless of the suspected cause of the event. Changes in conditions present at screening (defined as SV1 of the CVT-301-004E study for CVT-301-naïve and [CVT-301-009](#) patients and SV1 of the [CVT-301-004](#) study for [CVT-301-004](#) patients) and new symptoms, physical signs, syndromes, or diseases should be noted on the AE page of the eCRF during the study. For these AEs captured on the AE eCRF for CVT-301-naïve and [CVT-301-009](#) patients, AEs reported prior to the first study treatment at TV1 will be considered baseline AEs, and AEs reported from first treatment will be considered treatment-emergent adverse events (TEAEs).

AEs may be volunteered spontaneously by the patient, discovered as a result of general questioning by the study staff, or determined by physical examination. At each visit, the patient will be asked, “Have you experienced any problems since your last visit?” All AEs will be recorded on the eCRF. For all AEs, the investigator must pursue and obtain information adequate both to determine the outcome of the AE and to assess whether it meets the criteria for classification as a serious AE requiring immediate notification. Follow-up of the AE, even after the date of therapy discontinuation, is required if the AE persists until the event resolves or stabilizes at a level acceptable to the investigator.

In order to avoid vague, ambiguous, or colloquial expressions, all AEs should be recorded in standard medical terminology rather than the patient’s own words. Each AE will also be described in terms of duration, frequency, intensity, association with the study medication, assessment of possible causes, actions taken, and outcome, using choices given on the eCRF. Specific guidelines for classifying AEs by intensity and relationship to study medication are given in [Table 2](#) and [Table 3](#), respectively.

Table 2 Classification of Adverse Events by Intensity

MILD: An event that is easily tolerated by the patient, causing minimal discomfort and not interfering with everyday activities.

MODERATE: An event that is sufficiently discomfoting to interfere with normal everyday activities.

SEVERE: An event that prevents normal everyday activities.

Table 3 Classification of Adverse Events by Relationship to Study Medication

Definitely not related: The AE is definitely not related to the drug. This designation should be reserved for those events which occur prior to study treatment or for those events which cannot be even remotely related to study participation (e.g., injuries sustained in an automobile accident as a passenger).

Unlikely related: There is no reasonable association between the study treatment and the suspected event and the event could have been produced by the patient's clinical state or other modes of therapy administered to the patient.

Possibly related: The suspected adverse event may or may not follow a reasonable temporal sequence from study treatment administration but seems to be the type of reaction that cannot be dismissed as unlikely. The event could have been produced or mimicked by the patient's clinical state or by other modes of therapy concomitantly administered to the patient.

Probably related: The suspected adverse event follows a reasonable temporal sequence from study treatment administration, abates upon discontinuation of the treatment, and cannot be reasonably explained by the known characteristics of the patient's clinical state.

Definitely related: This designation should be reserved for those events which have no uncertainty in their relationship to treatment administration.

When changes in the intensity of an AE occur more frequently than once a day, the maximum intensity for the experience should be noted. If the intensity category changes over a number of days, then those changes should be recorded separately (with distinct onset dates).

11.1.9. Serious Adverse Events

A serious adverse event (SAE) is defined as any AE that meets 1 or more of the following criteria:

- The event results in death.
- The event is life-threatening.
- The event is permanently disabling (incapacitating or interfering with the ability to resume usual life patterns).
- The event results in unplanned inpatient hospitalization or prolongation of existing hospitalization.
- The event is a congenital anomaly.
- The event requires medical intervention of any kind in order to prevent any of the aforementioned outcomes.

A serious AE is not necessarily severe; for example, an overnight hospitalization for a diagnostic procedure must be reported as a serious AE even though the occurrence is not medically serious. By the same token, a severe AE is not necessarily serious: for example, nausea of several hours' duration may be rated as severe but may not be considered serious.

An SAE occurring during the study or within 4 weeks of stopping the treatment must be reported to the [REDACTED] and will be communicated to the Sponsor. **Any such SAE due to any cause, whether or not related to the study medication, must be reported within**

24 hours of occurrence or when the investigator becomes aware of the event. [REDACTED]

[REDACTED]

The event must also be recorded on the standard AE eCRF. Preliminary reports of SAEs must be followed by detailed descriptions later on, including clear and anonymized photocopies of hospital case reports, consultant reports, autopsy reports, and other documents when requested and applicable. SAE reports must be made whether or not the investigator considers the event to be related to the investigational drug.

Appropriate remedial measures should be taken to treat the SAE, and the response should be recorded. Clinical, laboratory, and diagnostic measures should be employed as needed in order to determine the etiology of the problem. The investigator must report all additional follow-up evaluations to the [REDACTED] within 10 calendar days. All SAEs will be followed until the investigator and Sponsor agree the event is satisfactorily resolved.

11.1.10. Suspected Unexpected Serious Adverse Reactions

Adverse events which meet all of the following criteria will be classified as suspected unexpected serious adverse reactions (SUSARs) and will be reported to the appropriate regulatory authorities in accordance with applicable regulatory requirements for expedited reporting:

- Serious
- Unexpected (i.e., is not consistent with the applicable product information such as the investigator's brochure for an unapproved investigational product or summary of product characteristics or product insert for an authorized product)
- There is at least a reasonable possibility that there is a causal relationship between the event and the medicinal product.

It is the Sponsor's responsibility to report SUSARs to the IRBs, IECs, and regulatory agencies in each country, although this responsibility may be delegated to the CRO. The procedures for notifying the health authorities and the IRBs/IECs of all SAEs/SUSARs (as appropriate) will be documented in the CRO study-specific and Sponsor standard operating procedure (SOP). SUSARs will be reported to the appropriate health authorities within 7 or 15 days (as appropriate).

11.1.11. Other Significant Adverse Events

To ensure patient safety, the investigator should also notify the medical monitor should any AE occur that is considered significant but does not meet criteria for an SAE, or that is considered unexpected. An unexpected AE is an AE that is not identified in nature, intensity, or frequency in the investigational drug brochure. The medical monitor and/or Sponsor may then choose to discontinue the patient from the study. In addition, any field monitor who notes a significant AE

or medical condition while reviewing the eCRFs or source documents at the site must immediately convey this information to the medical monitor.

11.1.12. Other Safety Assessments

11.1.12.1. UPDRS Part 4 and Examiner-Rated Dyskinesia

The UPDRS Part 4 is an assessment of potential complications of PD therapies. Questions 32-35 (related to dyskinesias) and 36-39 (related to clinical fluctuations) only will be completed as indicated in the time and events tables in [Appendix 2](#) through [Appendix 10](#). The baseline assessment for CVT-301-naïve and [CVT-301-009](#) patients will be completed at TV1. The baseline assessment for [CVT-301-004](#) patients will have been completed at TV1 of [CVT-301-004](#) study.

Additionally, during the post-dosing follow-up period at TV2, TV3, TV4, TV5, and TV6, the examiner will observe the patient for the appearance of dyskinesia during the 60-minute post-dose period and the maximum severity (mild, moderate, or severe) of any dyskinesia in the 60-minute post-dose period will be noted in the eCRF. The examiner will also note if the patient converts to the ON state during the 60-minute post-dose period and if so, whether the patient is still in the ON state at 60 minutes post-dose.

11.1.12.2. Columbia-Suicide Severity Rating Scale

The C-SSRS is a measure of suicidal ideation and behavior. The rating scale has 4 general categories: suicidal ideation, intensity of ideation, suicidal behavior, and actual attempts. For CVT-301-naïve and [CVT-301-009](#) patients, an initial baseline version will be given at SV2, and for all patients, a “since last visit” version will be given at all treatment visits to detect any emergence of suicidal ideation or behavior. [CVT-301-004](#) patients will have completed the baseline version during TV1 of the [CVT-301-004](#) study. The clinic staff should address any emerging neuropsychiatric needs in the event that the C-SSRS indicates active suicidal ideation.

Additional assessments of the C-SSRS will be completed as indicated in the time and events tables in [Appendix 4](#) through [Appendix 10](#). The self-report version of the C-SSRS will be completed at home during the withdrawal assessment period.

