10.1.4. Sub-Study to Assess Potential Withdrawal Symptoms

After patients are consented to protocol Version 5.2, they will participate in a withdrawal symptom sub-study at the end of TV4, TV5, or TV6, depending on which of the visits is the next scheduled one for the patient. In addition to the assessments detailed in the previous sections for the treatment visit, the AWQ and DDS-PC will be performed upon arrival in the ON state, and the UPDRS Part 1 will be performed preferably in the ON state.

When study activities for the visit are completed, patients will begin a 28-day period of assessment of potential drug withdrawal symptoms. To this end, patients who are at TV4 or TV5 at the time of consent will go on a study drug holiday for this time period. All patients in the withdrawal sub-study (patients consented to protocol Version 5.2) will be given copies of the AWQ, the DDS-PC, PHQ-9, Epworth Sleepiness Scale, C-SSRS (self-report version), and the self-administered MDS-UPDRS Parts 1B and 2 (Movement Disorder Society -UPDRS) to be completed at home at 1, 3, 6, 8, 11, 14, 17, 24, and 28 days after the treatment visit. Patients should fill out the questionnaires during their first ON state (after the intake of their first scheduled dose of standard oral PD medication) on each of these days. The site will call patients

at 14 (± 3) days after the treatment visit to remind them to complete the questionnaires, and to inquire about potential adverse events and changes in concomitant medications. Patients who enter the withdrawal sub-study after TV6 will also receive a call at 28 (± 3) days.

Patients who entered the study drug holiday will be scheduled to return to the clinic for a drug re-supply visit (see [Section 10.1.4.1](#)), and resumption of the full course of study treatment. Patients who entered the withdrawal sub-study after TV6 will be completed with the study after they return the questionnaires and undergo the DLco and spirometry assessment 4 to 5 weeks after completion of TV6, as described in [Section 10.1.3.9](#).

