²DLco and spirometry are to be performed in a dedicated pulmonary facility and includes slow vital capacity maneuver, DLco, and spirometry.

³Patients who withdraw early will undergo all of the TV6 assessments (except the pre-TV6 DLco and spirometry assessment) at the time of withdrawal. They will be scheduled to undergo the post-TV6 DLco and spirometry assessments 4-5 weeks following completion of the Early Withdrawal Visit.

⁴For patients who begin the study drug holiday at the end of this visit. Also dispense copies to be completed at home at 1, 3, 6, 8, 11, 14, 17, 24, and 28 days after TV6/ET. Complete in ON state after intake of first scheduled dose of standard oral PD medication. The self-report version of the C-SSRS and self-administered MDS-UPDRS Parts 1B and 2 will be dispensed for the post TV6 time points.

⁵Preferably in the ON state, but these must be performed before any other study evaluation.

⁶Assessment can be done at any point after arrival and before dosing.

⁷Document whether patient is fasting (≥ 4 hours after last snack or meal).

⁸If applicable, site staff will call the patient at 14 (± 3) days and 28 (± 3) days after TV6/Early Withdrawal to remind them to complete and return the withdrawal questionnaires, and to inquire about potential adverse events and changes in concomitant medications.

**Appendix 11: Time and Events Table-Treatment Visit (TV) 4.1 and TV5.1 for all Patients
(28 days+1 week] after TV4 or TV5)***

Procedures	
Collect completed questionnaires	X
Record any changes in usual PD medication dose/regimen	X
Record any changes in other concomitant medications	X
Record any adverse events	X
Distribute study drug kits	X
Review inhaler training (if needed)	X
Distribute PD Diary and Inhaled Dosing Log; review instructions for completion (if not done at prior visit)	X

*To occur 28 days (+1 week) after TV4 or TV5 (depending on when the patient begins the study drug holiday)

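### No step in the protocol has site staff see the at-home self-report C-SSRS before the forms come back, 28 to 35 days after TV4/TV5 or at an unstated time after TV6

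*Protocol*

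**What the plan says.** Protocol section 11.1.12.2 first describes the C-SSRS as given at visits: a baseline version, then a version covering the time since the last visit. It then states: "The clinic staff should address any emerging neuropsychiatric needs in the event that the C-SSRS indicates active suicidal ideation". Its second paragraph adds: "The self-report version of the C-SSRS will be completed at home during the withdrawal assessment period". The response sentence sets no time limit and does not exclude the self-report version.

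Section 10.1.4 describes the home period. "All patients in the withdrawal sub-study (patients consented to protocol Version 5.2) will be given copies of the AWQ", and the same list includes the self-report C-SSRS. The forms are to be "completed at home at 1, 3, 6, 8, 11, 14, 17, 24, and 28 days after the treatment visit". No electronic capture or alert is described.

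How the forms come back depends on when the patient enters:

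- **Holiday after TV4 or TV5.** The re-supply visit in section 10.1.4.1 begins with "Collect completed questionnaires". Appendix 11 times that visit: "To occur 28 days (+1 week) after TV4 or TV5 (depending on when the patient begins the study drug holiday".
- **After TV6.** "Patients who entered the withdrawal sub-study after TV6 will be completed with the study after they return the questionnaires" and have had the last lung function tests. Those tests are timed at 4 to 5 weeks; the return of the forms is not.
- **Early withdrawal.** Under section 10.1.5, patients who have not yet done the sub-study complete the same 28-day assessments.

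The site telephones every sub-study patient at Day 14 (±3) "to remind them to complete the questionnaires, and to inquire about potential adverse events and changes in concomitant medications". Patients entering after TV6 get a second call at Day 28 (±3). Appendix 10 applies both calls to early withdrawal as well and adds a reminder to return the forms. SAP section 9.9 plans shift tables for these data.

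**The concern.** The sub-study stops the inhaled drug to look for withdrawal symptoms and asks about suicidality nine times in 28 days. At treatment visits the scale is completed with staff present. In the home period the number of C-SSRS assessments rises, but no described step brings the answers to the site before the forms are handed in. A patient could mark active ideation on Day 1 and, with the plan followed to the letter, nobody at the site would know until the forms arrive.

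This is an individual patient-safety matter; no estimate, analysis set or primary endpoint depends on it. The protocol treats the risk as important: recent suicidal ideation or attempt is excluded (section 8.2, criterion 5). It also states prompt review for other off-site safety data: section 11.1.6 has a pulmonologist check pulmonary-laboratory spirometry at once for safety signals. The home C-SSRS has no counterpart.

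**Working it through.** **1. Inputs.** Completion days: 1, 3, 6, 8, 11, 14, 17, 24, 28, which is nine forms (section 10.1.4). Collection for holiday patients: Day 28 to 28 + 7 = 35 after TV4 or TV5 (Appendix 11). Calls: Day 14 (±3), so Day 11 to 17; after TV6 or early withdrawal also Day 28 (±3), so Day 25 to 31.

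**2. Wait per form, holiday patients.** Wait = collection day − completion day.

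| Form | Collected Day 28 | Collected Day 35 |
|---|---|---|
| Day 1 | 27 | 34 |
| Day 3 | 25 | 32 |
| Day 6 | 22 | 29 |
| Day 8 | 20 | 27 |
| Day 11 | 17 | 24 |
| Day 14 | 14 | 21 |
| Day 17 | 11 | 18 |
| Day 24 | 4 | 11 |
| Day 28 | 0 | 7 |

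Mean wait: 140/9 = 15.6 days to 203/9 = 22.6 days. Forms waiting at least 14 days: six with collection on Day 28, seven with collection on Day 35.

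**3. After TV6 or early withdrawal.** No return date is given, so the wait cannot be computed.

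**4. Forms already due at each call.** First call: five on Day 11, six on Day 14, seven on Day 17. Second call: eight on Day 25, nine on Day 28 or 31. The calls fall at useful times, but their stated content leaves the answers out.

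**5. At collection.** Section 10.1.4.1 and Appendix 11 list collecting the forms but no reading of them and no C-SSRS at that visit. The next scheduled C-SSRS at a visit is TV5 for a TV4 holiday (Week 36 against Week 24, nominally 12 weeks after TV4) or TV6 for a TV5 holiday (Week 56 or 60 against Week 36, nominally 20 to 24 weeks after TV5).

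**6. If the calls covered answers to date.** Assume each form due by the call day is complete. With the first call on Day *c*, the Day 1 form waits *c* − 1 days, and the first form after the call waits until collection.

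| Call day | Day 1 form | Next form, collected Day 28 / Day 35 | Longest wait |
|---|---|---|---|
| 11 | 10 | Day 14: 14 / 21 | 14 / 21 |
| 14 | 13 | Day 17: 11 / 18 | 13 / 18 |
| 17 | 16 | Day 24: 4 / 11 | 16 / 16 |

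The longest wait falls from 27 to between 13 and 16 days (collection Day 28), or from 34 to between 16 and 21 (collection Day 35). After TV6, with both calls used, no form due by the second call waits more than 17 days (Day 14 form, calls on Days 11 and 31: 31 − 14). A second call before Day 28 leaves the Day 28 form outstanding.

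**The case against.** A reader might infer more than the documents support.

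- **That the sections contradict each other.** They do not. Section 11.1.12.2 says staff *should* respond and gives no time limit. Staff who read the forms on collection and then respond comply with both sections. The fault is an unspecified step.
- **That staff cannot act during the 28 days.** The calls ask about adverse events, which section 11.1.8 defines to include any symptom that emerges or worsens. Section 10.1.6 allows unscheduled visits, and serious events within 4 weeks of stopping are reportable (section 11.1.9). These channels stand, but they depend on the patient raising the matter and do not use the scale. Holiday patients have one such scheduled call before the re-supply visit.
- **That the home form fails its stated detection purpose.** That purpose is stated for the since-last-visit version. Applying the response sentence to the home form is a reasonable reading because no version is exempted, but the text does not say so expressly.
- **That every form waits 28 to 35 days.** That interval runs from the treatment visit. The wait from completion is 0 to 34 days, and only holiday patients have a dated collection visit.
- **That PHQ-9 answers carry the same duty.** Section 11.2.4 attaches no response to them.

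Two further points are fair. That forms go unread until collected is inferred from silence: the form, call script and any site manual are not available here, and they may contain instructions. Also, only the inhaled adjunct stops; the usual Parkinson's regimen continues and oral as-needed medication is allowed during the holiday (section 9.4.2). Neither point supplies the missing step in the protocol, whose own list of call topics omits the answers.

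**Conclusion.** The point holds as a gap in the described process. Nothing in the protocol has site staff see home C-SSRS answers before the forms are collected at Day 28 to 35 after TV4 or TV5, or returned at an unstated time after TV6 or early withdrawal. For holiday patients a positive answer could go unseen for up to 34 days, with a mean wait per form of 15.6 to 22.6 days; after TV6 or early withdrawal the wait has no stated limit.

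This rests on four assumptions: forms are completed on the scheduled days; the re-supply visit falls within its window; no document outside the protocol and SAP provides earlier review; and the response sentence in section 11.1.12.2 extends to the self-report version. Because the matter is patient safety and the remedy is cheap, it merits correction although no statistical result depends on it.

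**What to change.** Reconcile section 11.1.12.2 with sections 10.1.4 and 10.1.4.1 and Appendices 8 to 11 so that home C-SSRS answers reach site staff during the 28 days. One way is to add the C-SSRS answers to date to the stated content of the calls already scheduled at Day 14 (±3) and, after TV6 or early withdrawal, Day 28 (±3). As shown above, this shortens the longest wait but does not remove it, so the text should also say when forms completed after the last call are read. State when and how forms are returned after TV6 or early withdrawal.

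The cost is protocol and call-script wording and a few minutes in each existing call, with no added visit. How staff respond to a positive answer is for the sponsor to set, and nothing is proposed on that here.
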